6.2.1. Preparation and Dispensing

Within this protocol, preparation refers to the investigator site activities performed to make the study intervention ready for administration or dispensing to the participant by qualified staff. Dispensing is defined as the provision of study intervention, concomitant treatments, and accompanying information by qualified staff member(s) to a healthcare provider, participant in accordance with this protocol. Local health authority regulations or investigator site guidelines may use alternative terms for these activities.

A qualified staff member will dispense the study intervention using the IRT system via unique container numbers in the blister cards provided, in quantities appropriate according to the [SOA](#). The participant should be instructed to maintain the product in the blister cards provided throughout the course of dosing and return the blister cards to the site at the next study visit.

6.3. Measures to Minimize Bias: Randomization and Blinding

6.3.1. Allocation to Study Intervention

Allocation of participants to treatment groups will proceed through the use of an IRT system (IWR). The site personnel (study coordinator or specified designee) will be required to enter or select information including but not limited to the user's ID and password, the protocol number, and the participant number. The site personnel will then be provided with a treatment assignment, randomization number, and DU or container number when study intervention is being supplied via the IRT system. The IRT system will provide a confirmation report containing the participant number, randomization number, and DU or container number assigned. The confirmation report must be stored in the site's files. Study intervention will be dispensed at the study visits as summarized in the [SOA](#). Returned study intervention must not be redispensed to the participants.

A randomization code using the method of random permuted blocks will be utilized to randomize eligible participants in 1:1:1:1 ratio (1 of 3 active dosing regimens of PF-06882961 or placebo) prior to the first dose of study intervention.

Participants will receive the following number of tablets and corresponding dose level described in [Table 4](#).

Table 4. Dose Levels in Study C3421015

Dose Level Description (dosed BID)	Number of PF-06882961 tablets			Number of PF-06882961-matching placebo tablets
	10 mg	40 mg	100 mg	10/40/100 mg
Placebo	-	-	-	3
PF-06882961 – 10 mg	1	-	-	2
PF-06882961 – 20 mg	2	-	-	1
PF-06882961 – 40 mg	-	1	-	2
PF-06882961 – 60 mg	2	1	-	-
PF-06882961 – 80 mg	-	2	-	1
PF-06882961 – 100 mg	-	-	1	2
PF-06882961 – 120 mg	2	-	1	-

The study-specific IRT reference manual and IP Manual will provide the contact information and further details on the use of the IRT system.

6.3.2. Breaking the Blind

The IRT will be programmed with blind-breaking instructions. In case of an emergency, the investigator has the sole responsibility for determining if unblinding of a participant's treatment assignment is warranted. Participant safety must always be the first consideration in making such a determination. If the investigator decides that unblinding is warranted, the investigator should make every effort to contact the sponsor prior to unblinding a participant's treatment assignment unless this could delay further management of the participant. If a participant's treatment assignment is unblinded, the sponsor must be notified within 24 hours after breaking the blind. The date and reason that the blind was broken must be recorded in the source documentation and CRF.

The study-specific IRT reference manual and IP Manual will provide the contact information and further details on the use of the IRT system.

Blood specimens will be obtained from all participants for PK analysis to maintain the study blind at the investigator site. The investigator site staff and blinded study monitor, if assigned, will be blinded to study treatment. Other specified Pfizer personnel will be unblinded to study treatment in order to permit interpretation of the safety, tolerability, PK CCI data while the study is ongoing. The blinded study monitor, if assigned, will remain blinded to treatment until all monitoring for the study has been completed. Specimens from participants randomized to placebo will not be routinely analyzed. To minimize the potential for bias, treatment randomization information will be kept confidential by Pfizer unblinded personnel and will not be released to the blinded investigator or blinded investigator site personnel until the study database has been locked or the investigator requests unblinding for safety reasons.

6.4. Study Intervention Compliance

When participants are dosed at the site, they will receive study intervention directly from the investigator or designee, under medical supervision. The date and time of each dose

administered in the site will be recorded in the source documents and recorded in the CRF. Study site personnel will examine each participant's mouth to ensure that the study intervention was ingested.

When participants self-administer study intervention at home, compliance with study intervention will be assessed at each visit. Compliance will be assessed by counting returned tablets during the site visits and documented in the source documents and CRF. Deviation(s) from the prescribed dosage regimen should be recorded in the CRF. At each visit from V3 to V10, sites should assess the blister cards for compliance. Compliance (as assessed by tablet count) will be defined as self-administration, by the participants of $\geq 80\%$ of the study supplied study intervention from Day 1 through Week 8, inclusive. Investigators must closely follow non-compliant, randomized, participants in order to enhance their adherence to treatment.

Any participant who fails to meet the criterion of $\geq 80\%$ compliance will be re-educated by the site staff on the importance of compliance with study intervention.

A record of the number of study intervention tablets dispensed to and taken by each participant must be maintained and reconciled with study intervention and compliance records. Intervention start and stop dates, including dates for intervention delays and/or dose reductions, will also be recorded in the CRF.

6.5. Concomitant Therapy

Participants in this study will be allowed to be on certain concomitant medications that have been prescribed. Attempts should be made not to alter the doses and regimens of the background medications after randomization and for the duration of participation in this study, except in circumstances where a change in dose is deemed medically necessary. Any changes must be captured in the CRF. Additionally, many over-the-counter medications are also permitted during this study.

See [Appendix 8](#) for details regarding prohibited concomitant medications. Sites are encouraged to contact the sponsor should there be questions as to whether a medication is permitted or prohibited.

Hormonal contraceptives that meet the requirements of this study are allowed to be used in participants who are WOCBP (see [Appendix 4](#)).

All concomitant treatments taken during the study must be recorded with indication, daily dose, and start and stop dates of administration. All participants will be questioned about concomitant treatment at each clinic visit.

Treatments taken within 28 days before the first dose of study intervention will be documented as a prior treatment. Treatments taken after the first dose of study intervention will be documented as concomitant treatments.

6.5.1. Medications for Glycemic Control

The use of other medications for glycemic control is not permitted in this study (see [Appendix 8](#)).

6.5.2. Antihypertensive Medications

The use of background antihypertensive agent(s) is permitted unless otherwise noted in [Appendix 8](#). Doses of antihypertensive agent(s) must be stable for at least 4 weeks prior to screening and throughout the study, except in circumstances where a change in dose is deemed medically necessary. Any changes in doses of these medications must be captured in the CRF.

6.5.3. Lipid Modifying Medications

The use of background lipid modifying agents is permitted unless otherwise noted in [Appendix 8](#). Doses of such lipid modifying agents must be stable for at least 4 weeks prior to screening and throughout the study, except in circumstances where a change in dose is deemed medically necessary. Any changes in doses of these medications must be captured in the CRF.

6.5.4. Management of Nausea and Vomiting

Nausea and vomiting have been reported with administration of GLP-1R agonists. Participants complaining of nausea may be managed conservatively with bed rest and/or fluid management at the discretion of the investigator. If the nausea and vomiting are not amenable to conservative management, anti-emetics may be administered at the investigator's discretion with notification to the sponsor and entry in the CRF.

6.5.5. Rescue Medicine

There is no rescue therapy to reverse the AEs observed with study intervention; standard medical supportive care must be provided to manage the AEs. Standard medical supportive care must be provided to manage the AEs, including administration of carbohydrates to treat HAE (see [Section 8.2.5.2.1](#)). Please also see [Section 8.2.5.2](#) and [Section 8.2.5.3](#) for management of hypoglycemia and hyperglycemia, respectively.

6.6. Dose Modification

Dose titration schemes are utilized for each study intervention dosing arm in this study as described in [Section 6.1.1](#). However, each dosing regimen will be provided in blister packs, and dose adjustment, either during dose titration or steady state dosing, will not be permitted per protocol.

6.7. Intervention After the End of the Study

No intervention will be provided to study participants at the end of the study.

7. DISCONTINUATION OF STUDY INTERVENTION AND PARTICIPANT DISCONTINUATION/WITHDRAWAL

7.1. Discontinuation of Study Intervention

In rare instances, it may be necessary for a participant to permanently discontinue study intervention (definitive discontinuation). Reasons for definitive discontinuation of study intervention include the following:

- Criteria for a potential DILI (Hy's law) case are met (see [Appendix 6](#));
- Intent to become pregnant or pregnancy confirmed by serum β -hCG testing;
- Safety or tolerability concern arises, in particular if not responsive to symptomatic management, dosing with double-blind study intervention may be stopped in an individual participant at the discretion of the investigator.

If the criteria for permanent discontinuation are met, the site should notify the sponsor Medical Monitor or sponsor Clinician.

If study intervention is definitively discontinued, the participant will not remain in the study for further evaluation. See the [SOA](#) for data to be collected at the time of discontinuation of study intervention.

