Days Relative to Dosing on Day 1 ^b	-28 to -3	Day -2 to Day 1	2	8	15	22	29	36	43	50	Day 55 to Day 56	57	58	63 - 70 84 - 91	
FSH (females only)	x														
HIV, HepBsAg, HepBcAb, HCVAb, syphilis	x														
Pregnancy test (females only)	x		x	x	x	x	x	x	x	x		x	x		
PF-06882961 PK ⁱ		x		x		x		x	x	x		x	x		
CCI															c
Urine Sampling for:															
Urine drug test	x														
Urinalysis (and microscopy, as appropriate)	x			x		x		x	x	x		x	x		
On-site urine pregnancy test (females only) ^j			x	x	x	x	x	x	x	x		x	x		

- a. Contact may occur via telephone and must occur 28 to 35 days from administration of the final dose of study intervention.
- b. Allowable time window for V3-V10 is ± 1 .
- c. Review glucometer and glucose log only.
- d. Physical examination may be performed at non-specified visits if there are findings during the previous exam or new/open AEs, if appropriate and at investigator discretion.
- C** f. Includes blood pressure and pulse rate; vital signs at Follow up, and early termination visit (if appropriate) are single; Triplicate vital signs should be conducted at Screening, prior to AM dose at 0H and at approximately 4H after AM dose on Days 8, 15, 22, 29, 36, 43, and 50. On Day 57, triplicate vital signs collected at 0H only. When a meal or snack is scheduled at the same time as vital signs, vital signs must be obtained prior to the meal/snack (See [Appendix 9](#)).
- g. 12-lead ECG at Screening, Days 15 and 43, Follow up, and early termination visit (if appropriate) are single; Triplicate ECGs should be conducted prior to AM dose at 0H and at approximately 4H after AM dose on Day 29. On Day 57, triplicate ECGs collected at 0H only. When a meal or snack is scheduled at the same time as an ECG, the ECG must be performed prior to the meal/snack (See [Appendix 9](#)).
- h. During inpatient stays, both AM and PM dosing will occur on the study site, except discharge day (Day 2). On outpatient visit and discharge day, AM dosing will occur at the study site, if applicable.
- i. PK samples to be collected prior to AM dose and at 4H after AM dose on Days 15, 29, and 43. Day 2 sample to be collected at 24H after AM dose on Day 1. Day 50 sample to be collected at 24H after AM dose on Day 49. Day 57 sample to be collected at 24H and 36H after AM dose on Day 56. Day 58 sample to be collected at 48H after AM dose on Day 56.

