7.2. Participant Discontinuation/Withdrawal From the Study

A participant may withdraw from the study at any time at his/her own request. Reasons for discontinuation from the study include the following:

- Refused further follow-up;
- Lost to follow-up;
- Death;
- Study terminated by sponsor;

At the time of discontinuing from the study, if possible, an early discontinuation visit should be conducted. See the [SOA](#) for assessments to be collected at the time of study discontinuation and follow-up and for any further evaluations that need to be completed.

The early discontinuation visit applies only to participants who are enrolled/randomized and then are prematurely withdrawn from the study. Participants should be questioned regarding their reason for withdrawal.

The participant will be permanently discontinued both from the study intervention and from the study at that time.

If a participant withdraws from the study, he/she may request destruction of any remaining samples taken and not tested, and the investigator must document any such requests in the site study records and notify the sponsor accordingly.

If the participant withdraws from the study and also withdraws consent (see Section 7.2.1) for disclosure of future information, no further evaluations should be performed and no additional data should be collected. The sponsor may retain and continue to use any data collected before such withdrawal of consent.

Lack of completion of all or any of the withdrawal/early termination procedures will not be viewed as protocol deviations so long as the participant's safety was preserved.

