7.2.1. Withdrawal of Consent

Participants who request to discontinue receipt of study intervention will remain in the study and must continue to be followed for protocol-specified follow-up procedures. The only exception to this is when a participant specifically withdraws consent for any further contact with him or her or persons previously authorized by the participant to provide this information. Participants should notify the investigator in writing of the decision to withdraw consent from future follow-up, whenever possible. The withdrawal of consent should be explained in detail in the medical records by the investigator, as to whether the withdrawal is only from further receipt of study intervention or also from study procedures and/or posttreatment study follow-up, and entered on the appropriate CRF page. In the event that vital status (whether the participant is alive or dead) is being measured, publicly available information should be used to determine vital status only as appropriately directed in accordance with local law.

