8.3.1. Time Period and Frequency for Collecting AE and SAE Information

The time period for actively eliciting and collecting AEs and SAEs (“active collection period”) for each participant begins from the time the participant provides informed consent, which is obtained before the participant’s participation in the study (ie, before undergoing any study-related procedure and/or receiving study intervention), through and including a minimum of 28 calendar days, except as indicated below, after the last administration of the study intervention.

Follow-up by the investigator continues throughout and after the active collection period and until the AE or SAE or its sequelae resolve or stabilize at a level acceptable to the investigator and Pfizer concurs with that assessment.

For participants who are screen failures, the active collection period ends when screen failure status is determined.

If the participant withdraws from the study and also withdraws consent for the collection of future information, the active collection period ends when consent is withdrawn.

If a participant definitively discontinues or temporarily discontinues study intervention because of an AE or SAE, the AE or SAE must be recorded on the CRF and the SAE reported using the CT SAE Report Form.

Investigators are not obligated to actively seek AE or SAE after the participant has concluded study participation. However, if the investigator learns of any SAE, including a death, at any time after a participant has completed the study, and he/she considers the event to be reasonably related to the study intervention, the investigator must promptly report the SAE to Pfizer using the CT SAE Report Form.

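### Protocol Section 7.1 removes participants from the study when dosing is definitively stopped, contradicting the 28-day adverse event collection rule in 8.3.1 and the 28 to 35 day contact in the Schedule of Activities

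*Protocol*

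**What the plan says.** Protocol 7.1 lists Hy's law criteria, pregnancy or intent to become pregnant, and safety or tolerability concerns as reasons for definitive discontinuation. It then says: "If study intervention is definitively discontinued, the participant will not remain in the study for further evaluation". It refers to the Schedule of Activities only for data due when dosing stops.

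Protocol 7.2, on early withdrawal, says: "The participant will be permanently discontinued both from the study intervention and from the study at that time". The same section points to the Schedule of Activities "for assessments to be collected at the time of study discontinuation and follow-up and for any further evaluations that need to be completed". It also says that incomplete withdrawal or early termination procedures are not deviations if the participant's safety was preserved.

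Protocol 8.3.1 runs active collection for each participant from consent "through and including a minimum of 28 calendar days, except as indicated below, after the last administration of the study intervention". The early ends it then gives are screen failure and withdrawal of consent. Definitive discontinuation appears only as a recording duty: "If a participant definitively discontinues or temporarily discontinues study intervention because of an AE or SAE, the AE or SAE must be recorded". The section adds: "Investigators are not obligated to actively seek AE or SAE after the participant has concluded study participation".

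Footnote a to Table 1, on the V12 contact, says: "Contact may occur via telephone and must occur 28 to 35 days from administration of the final dose of study intervention".

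Protocol 7.2.1 says: "Participants who request to discontinue receipt of study intervention will remain in the study and must continue to be followed for protocol-specified follow-up procedures". Its only exception is withdrawal of consent for further contact.

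**The concern.** The primary endpoint is the incidence of treatment-emergent AEs over the entire study. SAP 3.1.1 treats any AE starting within 365 days of the last dose as treatment emergent, so a new event in the 28 days after an early stop would count if it were collected. Whether it is collected depends on which section the site follows.

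The participants affected matter for the study's purpose. Down-titration is barred, and Protocol 6.1.1 says that those who cannot tolerate the scheme may have to stop dosing. Section 7.1 then takes them out of the study. Read with the statement in 8.3.1 that active seeking ends once participation has concluded, 7.1 could close AE collection at the early termination visit. With about 9 participants per arm, one participant is about 11% of an arm (1/9).

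The exposed part is narrow: new AEs arising between the early termination visit and 28 days after the last dose, mainly after tolerability stops. The AE that causes the stop is already counted.

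**Working it through.** **Comparing the rules for a participant stopped by the investigator for intolerance**

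| Source | Instruction |
|---|---|
| 7.1 | Leaves the study; data collected at the time of stopping |
| 7.2 | Out of both treatment and study at that time, but refers to the Schedule of Activities for follow-up |
| 8.3.1 | Active AE collection for at least 28 days after last dose; no exception for this participant |
| Table 1, footnote a | Contact required 28 to 35 days after final dose |

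A participant who personally asks to stop without withdrawing consent for contact comes under 7.2.1 and stays in follow-up. The conflict with 7.2.1 is limited to those participants.

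**Reproducing the plan's V12 window**

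For a completer the last dose is on Day 56. Then 56 + 28 = 84 and 56 + 35 = 91, which matches Day 84-91 in Protocol 4.1. Footnote a is worded relative to the final dose, so the window moves for early stoppers: a last dose on Day 14 gives Day 42-49, and one on Day 28 gives Day 56-63.

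**How many participants could be affected**

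Inputs: 36 randomized, 27 active and 9 placebo (Protocol 4.1). In C3421002, 98 were randomized 3:1 for 28 days, with 2 discontinuations for treatment-related TEAEs (Protocol 2.2.2 and 2.2.2.1). Since 27:9 is also 3:1, the overall rate can be applied directly.

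- Expected number: 36 × 2/98 = 0.73.
- Chance of at least one: 1 − (96/98)^36 = 0.52.
- Exact (Clopper-Pearson) 95% interval for 2/98: 0.25% to 7.18%. Times 36: 0.09 to 2.58 participants.
- If both earlier stops were on active drug (assumed): 98 × 3/4 = 73.5, and 27 × 2/73.5 = 0.73, the same figure.
- If the 28-day rate held over 56 days (assumed): 1 − (96/98)² = 4.04%, and 36 × 0.0404 = 1.45.

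These count treatment-related stops only. Section 7.1 covers any definitive stop.

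**What each could lose**

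Up to 28 days of active AE collection. The upper half-life in Protocol 2.2.2.2 is 8.09 h, so five half-lives is 5 × 8.09 = 40.5 h. Late new AEs would therefore mostly be unrelated to drug, but SAP 6.1.1 tabulates all-causality TEAEs as well as treatment-related ones.

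**The case against.** The best defence is that 8.3.1 already governs. It ties collection to the last dose rather than to study status, and for withdrawals it ends collection only when consent is also withdrawn. Section 7.1 mentions neither AE collection nor the V12 contact, so it can be read as cancelling only the remaining scheduled visits. The sentence about not actively seeking AEs may be meant for the period after V12. Footnote a uses mandatory wording, and 7.2 refers to follow-up in the Schedule of Activities. On this view a site would have to misread several passages before any AE was lost.

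This shows which rule should prevail, but it does not remove the contradiction. Sections 7.1 and 7.2 both say the participant leaves the study, 8.3.1 lifts the duty to seek AEs once participation has concluded, and 7.2 excuses missed early termination procedures. A site can follow that chain in good faith, and the missed contact might not be flagged.

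Much of the objection on size stands:

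- Known AEs are followed to resolution or stabilization (8.3.1, 8.3.3), clinically significant laboratory abnormalities are repeated (8.2.6), pregnancies are followed to outcome (8.3.5.1), and potential Hy's law cases are worked up (Appendix 6).
- The early termination visit has the same single ECG and vital signs as Follow-up, if appropriate (Table 1, footnotes f and g).
- The 2/98 rate comes from a 28-day study on background metformin, so applying it here is an assumption.
- The 365-day lag in the SAP classifies events; it creates no duty to collect them.

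**Conclusion.** The concern holds and should be fixed. The protocol gives opposite instructions on whether participants taken off drug are followed for new AEs, and AE incidence is the primary endpoint.

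The expected effect is small: about 0.7 participants at the earlier study's treatment-related stopping rate, or 1.5 if that rate held for 56 days. Both figures assume that the C3421002 rate transfers to this population. No change in TEAE incidence is estimated, because the documents give no rate of new AEs after stopping. This is a risk of under-recording and a gap in safety follow-up, not a demonstrated bias, and no formal inference depends on it.

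**What to change.** Replace the 7.1 sentence with wording to this effect:

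> Anyone whose study drug is definitively stopped, for whatever reason, completes the early termination visit and the V12 contact 28 to 35 days after the last dose. AEs and SAEs are collected through that contact under Section 8.3.1, unless consent for further contact is withdrawn.

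In 7.2, make the statement that the participant leaves the study subject to that contact. In 7.2.1, refer to 7.1 for the follow-up procedures. A site visit equivalent to V11 is optional and is not needed to resolve the conflict.

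The cost is one replaced sentence and two alignments in the protocol, with no SAP change. In practice it adds one telephone contact per early stopper, about one participant (0.7 to 1.5) at the rates above. Footnote a already requires that contact.
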